The specific aims of this pilot study are: **Aim 1)** *To identify whether no prep ready to eat meals (intervention) or ingredient bundles (control) have higher client acceptability, liking, satisfaction, and perceived diet quality ratings.* **Hypothesis:** No prep ready to eat meals will have higher client acceptability, liking, satisfaction, and perceived diet quality scores than ingredient bundles. **Rationale:** Previous research has shown that acceptance, liking, satisfaction, and perceived diet quality are important determinants of the foods people are willing to eat and the ultimate success of diet-related interventions¹². Aim 1 will establish which strategy is most acceptable and desirable for food pantry clients to inform the development of a future randomized-controlled trial that will aim to test which strategy is most effective at improving objective dietary quality and reducing health-related risk factors. **Aim 2)** *To identify whether no prep ready to eat meals (intervention) or ingredient bundles (control) have higher feasibility ratings with food pantry staff.* **Hypothesis:** No prep ready to eat meals will have higher feasibility ratings than ingredient bundles among pantry staff. **Rationale:** It's unclear how much staff time and pantry resources are needed to put together an ingredient bundle from a recipe or store no prep ready to eat meals in appropriate refrigeration units. This pilot study will determine the resources needed to carry out each program and determine which is preferable and feasible for the pantry staff that would be asked to carry out either model given that staff buy-in is a key component to intervention success¹³.

2. Background.

- Describe past experimental and/or clinical findings leading to the formulation of your study.
- For research involving investigational drugs, describe the previously conducted animal and human studies.
- For research that involves FDA approved drugs or devices, describe the FDA approved uses of this drug/device in relation to your protocol.
- Attach a copy of the approved labeling as a product package insert or from the Physician's Desk Reference.

You may reference sponsor's full protocol or grant application (section number and/or title) or if none, ensure background includes references.

Please respond to all components of this item, or clearly indicate which components are not applicable.

a. Background

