have cutting knives or a blender²⁶, these are kitchen tools frequently recommended for healthier meal preparation strategies and required to prepare many recipes, such as stir fries, smoothies, and casseroles.

No prep ready-to-eat meals alleviate the time and food preparation constraints faced by people experiencing food insecurity and provide the opportunity to encourage more nutritious food consumption in a potentially preferable package. While market research and consumer scientists have identified no prep ready-to-eat meals as a burgeoning food retail avenue²⁶, these meals have not been empirically tested as a strategy for improving food security, dietary quality, and health outcomes among clients in a food pantry setting. Given the novelty of this idea, formative research is needed to confirm the intervention is desirable to food pantry clients and feasible for food pantry personnel to carry out.

b. Current practice

[figure not shown]
Currently, food pantry clients at Crossroads receive food in one of three ways:

- 1) Emergency box filled with food provisions filled by pantry staff – the number of pounds received is dependent on the household size and age of household members, the pantry client does not get to choose the food they receive
- 2) With an appointment, clients walkthrough the pantry and select food off shelves and from inside refrigeration units based on a point system – points are distributed based on household size and age of household members and the pantry inventory, the pantry client chooses the food they receive
- 3) With an appointment, clients select food using a web-based application that displays live inventory. Clients select food using the application based on the same in-house point system, the pantry client chooses the food they receive

3. Study Design.

Describe the study design (e.g., single/double blind, parallel, crossover, etc.) Consider inserting a scheme to visually present the study design.

Figure 3. Proposed study design

To test the first hypothesis, I will use a randomized repeated measures between-subjects design with half of the participants randomized to receive 14-days of no prep ready-to-eat meals (intervention, n=35) and half of the participants randomized to receive 14-days of ingredient bundles (control, n=35) (Figure 3).

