To test the second hypothesis, I will use a mixed-methods approach with food pantry staff (N=10), including questionnaires with fixed and open-ended items on feasibility and satisfaction of each distribution strategy followed by 30-minute semi-structured 1-1 interviews conducted by UT Southwestern study staff.

4. Research Plan / Description of the Research Methods:

4.a. Provide a comprehensive narrative describing the research methods.

- 1) Provide the **order in which tests/procedures will be performed**,
- 2) Provide the **setting** for these events and a description of the **methods used to protect privacy** during the study.
- 3) Provide the **plan for data analysis** (include as applicable the **sample size calculation**)

Please respond to all components of this item, or clearly indicate which components are not applicable.

C.1.5 Intervention Methods

After completing consent forms, participants will be randomized to receive no prep ready-to-eat meals or ingredient bundles using random number generation. Participants will be unaware of their assignment until they are asked to select study meals, in which case it will be obvious because of the food items available to select. Participants will complete questionnaires and then select meals – they can select up to 2-meals, or the bundles needed to make 2-meals, for 14-days for themselves and 2 additional members of their household. Participants will elect to receive one week of meals after selection and come back to pick-up the second week of meals or they will take home all study meals at one time (participants choice). Participants will return at the end of the 2-week study period to complete the follow-up questionnaires and receive payment. A study timeline of intervention components and data collection is provided in **Table 1** to aid visualization of the study plan and timeline for **food pantry clients**.

Table 1. Study plan and timeline for food pantry clients.

Baseline appointment (Day 0)	Intervention (Day 1 - Day 14)	Follow-up appointment (Day 15)

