
 1. Informed consent 2. Randomization 3. Questionnaires (demographics, current pantry use, acceptability, satisfaction, liking, diet quality) 4. Selection of preferred no prep ready-to-eat meals OR ingredient bundles from the available study foods depending on study assignment 5. Follow-up appointment scheduled 	
 1. Participants and family members consume no prep ready-to-eat meals or ingredient bundles at-home for 14-days 2. Depending on the client's preference, reminder phone calls, texts, and/or emails are sent leading up to their follow-up appointment 	
 1. Questionnaires (demographics, current pantry use, acceptability, satisfaction, liking, diet quality) 2. Participant thank you and payment

C.1.5.1 No prep ready-to-eat meals

Roots Food Group provides nutrient-dense dietitian developed no prep ready-to-eat meals to many of the 14 million people on Medi-Cal in California through Aetna and HealthNet. The community-based 501c3 arm of Roots Food Group, Roots Food Foundation, provides the same meals and other resources to people living with blindness at no cost. Roots Food Foundation has agreed to donate and supply meals for this study.

Pantry clients will select study meals for up to 14-days' worth of meals for themselves and 2-members of their household using Crossroads online food selection platform (this platform is already built and is how clients currently select pantry foods). Roots Food Group produces over 70 meals. We have elected to study 14-days of meals to offer clients variety and determine which flavors are most desirable to clients. After ordering, meals will be retrieved from a refrigeration unit, boxed by pantry staff, and brought to the participant to take home. An example dinner is "Teriyaki Chicken with Roasted Potatoes and Broccoli", and an example breakfast is "Omelet with Peppers and Zucchini". Meals can be stored in a refrigerator or freezer and eaten immediately or after reheating depending on the meal and consumer preference. 94% and 86% of Crossroads clients reported owning a refrigerator and microwave respectively when previously surveyed²⁷ and microwaves are available in many community centers and gas stations for public use. This makes no prep ready-to-eat meals a potential solution to many of the challenges faced by Crossroads pantry clients and people experiencing food insecurity.

C.1.5.2 Ingredient bundles

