At the baseline appointment participants will complete informed consent and a questionnaire that includes demographics, typical food pantry utilization, satisfaction, acceptability, liking, and perceived diet quality. Satisfaction items will be adapted from previously validated food pantry client satisfaction surveys (e.g., "How satisfied are you with the amount/variety/frequency of food that you and others in your household receive at this food pantry?")²⁸. Possible responses range from very satisfied and somewhat satisfied to somewhat dissatisfied and very dissatisfied. Liking of study foods will be measured by showing the name and picture of the meal or ingredient bundle and asking participants to respond to a hedonic 9-point bipolar scale with four measures of liking and four measures of dislike and a neutral "neither like nor dislike" item²⁹. Acceptability will be measured by showing the name and picture of the meal and asking the client whether they and/or members of their household ate the meal within the past 2-weeks and whether they would select the meal again if given the opportunity in the future³⁰. Perceived dietary quality will be measured using a single validated item that asks participants to rate their overall diet quality as "excellent," "very good," "good," "fair," or "poor"³¹. At the follow-up appointment, participants will complete the same liking and acceptability ratings, and a similar satisfaction questionnaire and perceived diet quality item, except wording will be slightly modified to "How satisfied were you with the amount of food that you and others in your household received at the food pantry **in the past 2-weeks?**" "How would you rate your dietary quality **over the past 2-weeks?**". These measures will allow us to determine between-group

Form A

IRB # STU 2022-0809

differences at baseline as well as within- and between-group changes in acceptability, satisfaction, liking, and diet-quality after consuming meals over time. These measures will also identify client's preferred meal flavors and frequency as well as the quantity desired in a future intervention.

C.1.6.2. Pantry Staff Measures

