Food pantry staff will answer feasibility items for each of the intervention groups, such as desire to implement each food distribution strategy in the future, perceived appropriateness of the intervention given their organizational goals, perceived sustainability, and financial/staff resources needed to carry out the intervention longer term³². Staff participants will also respond to qualitative open-ended response items such as "Describe any challenges experienced with distributing ingredient bundles" "Describe any challenges experienced with distributing no prep ready-to-eat meals". Responses to the questionnaire will be followed with 30-minute semi-structured 1-1 interviews with study personnel, which give pantry staff the opportunity to directly voice any challenges or preferences that come up when implementing either approach. The pantry personnel perspective will allow us to design a feasible and sustainable longer-term intervention.

C.1.7. Analytic Plan

C.1.7.1. Analytic Plan for Pantry Client Data

Descriptive statistics (e.g., means, percentages, chi-squared tests of independence) will be used to describe participant characteristics and baseline differences. The independent variable of interest will be randomized group assignment (e.g., no prep ready to-eat-meals vs. ingredient bundles). Spearman's correlation and/or repeated measures Analysis of Variance (ANOVA) will be used to describe the association between group assignment and client's perceived diet quality at follow-up. If normally distributed, repeated-measures ANOVA is acceptable and will be used. If non-normal, Spearman's correlation will be used. For the other three outcomes of interest (satisfaction, acceptability, and liking) sum scores will be calculated, and model assumptions will be tested (e.g. residual distributions) before proceeding with repeated-measures Analysis of Variance (ANOVA) to test for group effects on study outcomes of interest and group-by-time interactions.

C.1.7.2 Analytic Plan for Pantry Staff Data

Descriptive statistics (e.g., means, percentages) will be used to describe quantitative items on staff feasibility and satisfaction. Qualitative thematic analysis of open-ended questionnaires and interviews will be synthesized into key findings and suggestions for future intervention development.

Form A

IRB # **STU 2022-0809**

4.b. List of the study intervention(s) being tested or evaluated under this protocol

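### Perceived diet quality: replace the normality-based switch between ANOVA and Spearman with one Day 0-adjusted comparison of the Day 15 rating

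*Combined protocol and SAP*

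**What the plan says.** Aim 1 states a directional hypothesis: "No prep ready to eat meals will have higher client acceptability, liking, satisfaction, and perceived diet quality scores than ingredient bundles". Section 3 (Study Design) gives the client design as "I will use a randomized repeated measures between-subjects design", with 35 clients per arm.

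C.1.6.1 defines the outcome: "Perceived dietary quality will be measured using a single validated item", with five ordered answers from excellent to poor. Table 1 lists "Questionnaires (demographics, current pantry use, acceptability, satisfaction, liking, diet quality" at both Day 0 and Day 15. C.1.6.1 changes the item between visits, from the diet overall to the diet of the preceding two weeks. It also says that the repeated measures will show change within and between groups, diet quality included.

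C.1.7.1 sets the analysis. Spearman's "correlation and/or repeated measures Analysis of Variance (ANOVA) will be used to describe the association between group assignment" and the client's rating at follow-up. The rule for choosing is: "If normally distributed, repeated-measures ANOVA is acceptable and will be used. If non-normal, Spearman's correlation will be used". The section then turns to satisfaction, acceptability and liking. Only for those three does it mention residuals as the thing to check, and only for them does it use ANOVA "to test for group effects on study outcomes of interest and group-by-time interactions".

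**The concern.** The rule does not name the normality check or its threshold. It does not say whether Day 0, Day 15, change or residuals are checked, and the *and/or* in the opening sentence is looser than the either/or that follows.

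The two branches also do different things. Spearman relates group to the Day 15 rating alone: it leaves out a Day 0 rating already collected, and returns a coefficient that cannot be read as a difference in rating points. The ANOVA branch uses both visits, but no term is named for this item.

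At stake is how well the pilot reports one of its four Aim 1 outcomes. Aim 1 is meant to inform a later randomised trial, and an estimated difference with a confidence interval serves that purpose better than a correlation coefficient.

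**Working it through.** The plan gives no figure for this outcome to reproduce. From the documents come 35 per arm, five categories, and ratings at Day 0 and Day 15. The two-sided 5% level, the effect sizes, the Day 0 to Day 15 correlation ρ and the rating shapes are all assumptions.

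**1. Which branch will be used?** Take Lilliefors on all 70 Day 15 ratings, with 5% critical value 0.886/√70 = 0.106. The statistic is the largest gap between the stepped distribution of the ratings and a continuous normal curve, so it is at least half the largest step. A category holding 15 of 70 gives at least (15/70)/2 = 0.107, which already rejects. Only exactly 14 in each category escapes this bound. There the mean is 3 and the SD 1.424, so the curve at rating 1 is Φ(−1.404) = 0.080 against a step to 0.200: a gap of 0.120, which also rejects. This check therefore always leads to Spearman.

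Other checks depend on shape. The table shows the percentage of samples in which normality is rejected (2,000 samples of 70 per shape, no group effect; SW = Shapiro-Wilk):

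| Assumed shape, % per category | SW | Lilliefors | Jarque-Bera | D'Agostino-Pearson | Abs. skewness or excess kurtosis > 1 | SW, group-centred residuals |
|---|---|---|---|---|---|---|
| 10/35/35/15/5 | 100 | 100 | 2.6 | 4.3 | 0.6 | 98.6 |
| 8/24/36/24/8 | 100 | 100 | 0.0 | 5.7 | 1.3 | 93.9 |
| 5/10/30/35/20 | 100 | 100 | 11.5 | 16.2 | 1.8 | 99.8 |
| 30/40/20/7/3 | 100 | 100 | 65.1 | 70.6 | 21.0 | 100 |
| 45/35/15/4/1 | 100 | 100 | 87.4 | 91.6 | 49.5 | 100 |
| 20 each | 100 | 100 | 15.0 | 99.5 | 95.2 | 100 |

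So the usual sensitive checks lead to Spearman. ANOVA is reached only through a less sensitive check and a favourable shape.

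**2. What would each ANOVA term estimate?** Let δ be the Day 15 group difference. Randomisation makes the arms equal at Day 0 in expectation. Group-by-time then estimates the difference in change, (δ − 0) = δ in expectation, but through a change score that carries the Day 0 noise in full. The group main effect estimates the average over both visits, (0 + δ)/2 = δ/2. Neither is a direct estimate of the follow-up difference, although the first is not biased for it.

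**3. What does using Day 0 buy?** Normal approximation: power = Φ(d/(f·√(2/35)) − 1.96), with √(2/35) = 0.239. The SD factor f is 1 for Day 15 alone, √(2(1−ρ)) for change, and √(1−ρ²) with Day 0 adjustment. For d = 0.5:

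- Day 15 alone: 0.5/0.239 = 2.092, and Φ(0.132) = 55% at any ρ.
- Change, ρ = 0.3/0.5/0.7: f = 1.183/1.000/0.775, power 42/55/77%.
- Adjusted for Day 0: f = 0.954/0.866/0.714, power 59/68/83%.

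**4. The same on a five-category item.** Correlated normal variables were cut into categories, 10,000 replicates per setting. Power for the shape 10/35/35/15/5 at ρ = 0.3/0.5/0.7:

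| Latent shift | Spearman, Day 15 | Group-by-time | ANCOVA |
|---|---|---|---|
| 0.5 SD | 50/49/50% | 38/48/65% | 53/59/73% |
| 0.6 SD | 64/65/65% | 51/63/80% | 69/74/86% |

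Over four shapes, both shifts and three correlations (24 settings), ANCOVA gains 2.0 to 22.6 points over Spearman, but only 2.0 to 4.7 at ρ = 0.3. At 0.5 SD in this shape, the mean 95% CI half-width in rating points is 0.47/0.44/0.38 for ANCOVA, against 0.49 for the unadjusted Day 15 difference.

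**5. Error rate.** With no effect, ANCOVA rejects in 4.7 to 5.3% of samples. A switch followed as written, with Jarque-Bera choosing between Spearman and group-by-time, rejects in 4.6 to 5.5% (two shapes, three correlations).

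**The case against.** A reader might infer that the plan leaves the target wholly open between a Day 15 association, a change and a two-visit average. The documents do not support that: C.1.7.1 places the association at follow-up, and those words govern both methods. What remains is narrower, namely that repeated-measures ANOVA does not directly estimate that target. The two-visit average fits the wording worst, so its low simulated power (19 to 32%) should carry little weight.

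A reader might also infer bias or an inflated false-positive rate. Spearman is valid under randomisation, and step 5 shows no inflation when the switch is followed as written. Step 5 does not cover choosing a method after seeing both results.

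Nor should much be made of how often the branches disagree. Spearman and group-by-time fall on opposite sides of 5% in 29 to 38% of simulated samples with an effect, but two tests of moderate power often do. ANCOVA and a Spearman sensitivity analysis disagree in 10 to 28%.

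The power gain rests on an unknown correlation, and the changed item wording could lower it. Finally, the plan's verb for this outcome is to describe, and the study is a pilot.

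All of this stands and limits the point. It does not remove it. Where Spearman is used, as is likely, the Day 0 rating still goes unused and no difference in rating points is reported, while Aim 1 states a directional hypothesis for this outcome.

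**Conclusion.** The point holds as a minor, cheap improvement. The switch most likely resolves to a valid Spearman test of the Day 15 rating, which is less informative than the data allow and does not supply the between-group change described in C.1.6.1. If it resolves to ANOVA, the term to be reported is not named for this item.

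Under the assumed shapes and a 0.5 to 0.6 SD shift with 35 per arm, Day 0 adjustment adds about 2 to 5 points of power over Spearman at a correlation of 0.3, and up to about 23 at 0.7. The case for one fixed, interpretable estimate does not depend on the larger figure. The point concerns one of four Aim 1 outcomes among 70 clients.

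**What to change.** In C.1.7.1, delete the *and/or* and the normality rule for perceived diet quality, and prespecify one Day 0-adjusted comparison. For example: ANCOVA of the Day 15 rating (scored 1 to 5) on group and Day 0 rating, reporting the adjusted mean difference with its 95% CI. The group coefficient is the same whether the response is the Day 15 rating or the change from Day 0, so one estimate serves both C.1.7.1 and the between-group change in C.1.6.1. Tabulate category counts by arm and visit to describe within-group change. Keep the Spearman (rank) test of the Day 15 rating as a sensitivity analysis.

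Costs:

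- ANCOVA treats the five categories as equally spaced. The rank test does not, and a proportional-odds model with the same terms would be an alternative.
- Diet quality would be modelled differently from the other three outcomes unless they too are baseline-adjusted. The plan should say which.
- Questionnaire order needs fixing as well as analysis wording. Day 0 questionnaires follow randomisation, and C.1.5 says "Participants will be unaware of their assignment until they are asked to select study meals". The liking item, however, shows pictures of the meal or the bundle, which may reveal the arm. Asking diet quality before those pictures keeps it a true baseline.

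No new data, visits or participants are needed.

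### Satisfaction: the plan does not say which ANOVA term answers Aim 1. The group main effect estimates half the Day 15 difference, and the interaction is usually less precise than Day 15 adjusted for Day 0.

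*Combined protocol and SAP*

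**What the plan says.** C.1.7.1 forms sum scores for satisfaction, acceptability and liking and checks model assumptions before "proceeding with repeated-measures Analysis of Variance (ANOVA) to test for group effects on study outcomes of interest and group-by-time interactions". It does not say which of the two terms decides. The Aim 1 hypothesis says only that scores will be higher with ready-to-eat meals; it names no visit and no model term. C.1.6.1 comes closest to a choice. It says the measures serve to determine, between groups, "differences at baseline as well as within- and between-group changes in acceptability, satisfaction, liking, and diet-quality after consuming meals over time".

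Three statements fix the status of the Day 0 satisfaction score:

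- **Content (C.1.6.1).** The example item is "How satisfied are you with the amount/variety/frequency of food that you and others in your household receive at this food pantry". It concerns the pantry's usual food, not the study food.
- **Sequence (Table 1, Day 0).** The order is "2. Randomization 3. Questionnaires (demographics, current pantry use, acceptability, satisfaction, liking, diet quality". C.1.5 agrees: "Participants will complete questionnaires and then select meals".
- **Awareness (C.1.5).** "Participants will be unaware of their assignment until they are asked to select study meals".

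Satisfaction is asked again at Day 15 with the reference period changed to the past two weeks, in the same way for both arms.

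**The concern.** The two terms in the sentence estimate different quantities. If the arms have the same expected satisfaction at Day 0, the group main effect mixes a visit at which no effect is possible with the visit at which the effect is measured. Group assignment is called the independent variable of interest and group effects are listed first, so a reader could take the main effect as the answer and understate the food strategy's effect by half.

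The interaction avoids this. With two visits, however, it is simply the between-arm difference in change scores. It carries the full noise of the Day 0 score even when that score predicts Day 15 only weakly. The pilot is meant to inform a later randomised trial from 35 clients per arm, so the size and interval of this estimate are what it has to deliver.

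**Working it through.** The plan states no power or sample-size figure for this outcome, so there is nothing to reproduce.

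**From the documents:** n = 35 per arm (Section 3); two visits, Day 0 and Day 15 (Table 1); expected Day 0 difference of zero (C.1.5, Table 1, C.1.6.1).

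**Assumed:** two-sided 5%; Day 15 difference d = 0.6 SD; correlation rho between visits from 0.3 to 0.8; equal SDs; full follow-up. The last two and d are varied below.

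**Formulas (unit SD):**

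- Group main effect: estimates (0 + d)/2 = d/2; variance (1 + rho)/n.
- Interaction: estimates d − 0 = d; variance 4(1 − rho)/n.
- Day 15 adjusted for Day 0 (ANCOVA): estimates d; large-sample variance 2(1 − rho²)/n.
- Variance ratio, interaction to ANCOVA: 4(1 − rho) / [2(1 − rho)(1 + rho)] = 2/(1 + rho).

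**Example, rho = 0.5, n = 35.** The SEs are √(1.5/35) = 0.207 (main effect), √(2/35) = 0.239 (interaction) and √(1.5/35) = 0.207 (ANCOVA). The estimates are 0.30, 0.60 and 0.60. Power is from the noncentral t with 68 df (67 for ANCOVA).

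In this table, brackets hold results simulated with the slope estimated (40,000 trials per setting). Half-widths are of the 95% CI, in SD units.

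| rho | Variance ratio | Power, main effect | Power, interaction | Power, ANCOVA | Half-width, interaction | Half-width, ANCOVA |
|---|---|---|---|---|---|---|
| 0.3 | 1.54 (1.52) | 34% | 55% | 74% (73.0%) | 0.56 | 0.46 |
| 0.5 | 1.33 (1.31) | 30% | 70% | 82% (81.1%) | 0.48 | 0.41 |
| 0.7 | 1.18 (1.17) | 27% | 89% | 93% (92.9%) | 0.37 | 0.34 |
| 0.8 | 1.11 (1.09) | 26% | 97.5% | 98.5% (98.4%) | 0.30 | 0.29 |

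Simulated mean estimates were 0.30 for the main effect and 0.60 for the other two. The halving concerns the estimate. The main effect's SE differs too, so its loss of power should be read from the table.

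**Loss to follow-up (assumed 20%, 28 completers per arm).** For rho 0.3, 0.5, 0.7 and 0.8, power for interaction vs ANCOVA is 46 vs 64%, 60 vs 72%, 81 vs 87% and 94 vs 96%. Half-widths are 0.63 vs 0.51, 0.54 vs 0.46, 0.42 vs 0.38 and 0.34 vs 0.32.

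**Smaller effect (d = 0.5, 35 per arm).** The same formulas give 41 vs 58%, 54 vs 66%, 76 vs 82% and 90 vs 93%. The half-widths and variance ratios do not depend on d.

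**Unequal SDs.** With k = Day 0 SD / Day 15 SD, the large-sample ratio is (k² + 1 − 2·rho·k)/(1 − rho²). The numerator exceeds the denominator by (k − rho)², so the ratio is never below 1. At rho = 0.5:

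- k = 1.25: 1.3125/0.75 = 1.75 (simulated 1.74)
- k = 0.75: 0.8125/0.75 = 1.08 (simulated 1.07)
- k = 0.5: 0.75/0.75 = 1.00 (simulated 0.98; power 81.5% for the interaction vs 80.9% for ANCOVA)

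Estimating the slope divides the ratio by about 1 + 1/(2n − 4) = 1 + 1/66 = 1.015. The worst case for ANCOVA is therefore a ratio of about 0.985, a loss of under 2% of variance.

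**Why this is confined to satisfaction.** C.1.6.1 states "Liking of study foods will be measured by showing the name and picture of the meal or ingredient bundle", so Day 0 liking may already differ by arm. Day 0 acceptability asks whether the household "ate the meal within the past 2-weeks and whether they would select the meal again if given the opportunity in the future", although no study meal has yet been supplied. With an assumed Day 0 gap of 0.3 SD, d = 0.6 and rho = 0.5, simulated means were 0.45 (main effect), 0.30 (interaction), 0.45 (ANCOVA) and 0.60 (Day 15 difference alone). Only the last recovers the Day 15 difference.

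**The case against.** The strongest reply is that the planned analysis already contains a valid test. The interaction is in the ANOVA, it matches the between-group changes described in C.1.6.1, and it is unbiased. The halving arises only if someone reads the main effect as the treatment effect, which no section says will happen. One sentence naming the interaction would remove that risk, leaving a choice between two valid analyses in a pilot. This stands as far as it goes: nothing here calls the interaction invalid. It does not remove the loss of precision. Below rho = 0.5 with equal SDs, the interaction is less precise even than the unadjusted Day 15 difference. High correlation cannot be presumed, because both the reference period and the food supplied change between visits.

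A second objection is that the zero Day 0 difference depends on item order. Table 1 lists acceptability before satisfaction and C.1.6.1 lists satisfaction first; neither is stated to be the order of administration. If arm-specific pictures came first, Day 0 satisfaction could be affected, and neither exact halving nor an unbiased interaction would be assured. This stands as a condition, and the fix addresses it.

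Third, every precision figure rests on assumed values, and the gain is slight at high correlation. That is correct, which is why ranges are shown.

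Finally, perceived diet quality is also measured at both visits and may be analysed by repeated-measures ANOVA. It has its own decision rule in C.1.7.1 and is not covered here.

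**Conclusion.** The point holds for satisfaction. No deciding term is named. The group main effect estimates d/2. The interaction is unbiased but usually less precise than Day 15 adjusted for Day 0. With equal SDs, its large-sample variance is 54% larger at rho 0.3, 33% at 0.5, 18% at 0.7 and 11% at 0.8.

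The halving rests on randomisation and on satisfaction being asked before clients can infer their arm. The precision figures rest on the assumed correlation and SDs, and the power figures also on the assumed effect. Unbiasedness further assumes that dropout does not differ by arm in a way related to the outcome. The change is worth making because it improves clarity and precision at almost no cost; the planned interaction is not invalid.

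**What to change.** In C.1.7.1:

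- Make the single Aim 1 contrast for satisfaction the Day 15 sum score regressed on group and Day 0 sum score, reported as an adjusted between-arm difference with its 95% CI.
- State that the group main effect over both visits will not be used as evidence of the food strategy's effect. Within-arm changes may still be described.

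In C.1.6.1:

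- State that the satisfaction items are asked before any study-food picture is shown.

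For the two neighbouring outcomes in the same sentence:

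- Liking: use the same model only if the baseline pictures are identical in both arms and rated before allocation is revealed; otherwise use the Day 15 between-arm difference.
- Acceptability: use the Day 15 between-arm difference.

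The cost is one paragraph of analysis wording and one sentence on questionnaire order and baseline pictures, which must then be followed when the questionnaire is given. Day 0 satisfaction is already collected, so no data, visits or participants are added.
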